6.1 Hypotheses

The null hypothesis for the primary effectiveness endpoint is that there is no difference in the mean change in PAL for the treatment and control arms (indicating equality). Rejection of the null hypothesis

indicates the observed data supports the alternative hypothesis that a difference in the mean change in PAL exits between the treatment and control arms (indicating inequality). The hypotheses associated with the primary effectiveness endpoint are:

H₀:
$$\mu_t - \mu_c = 0$$

H₁: $\mu_t - \mu_c \neq 0$

where μ_t and μ_c are the mean changes in PAL for the treatment and control arms, respectively.

6.2 Sample Size

The following assumptions were made while determining the required sample size:

- Patients will be assigned to either the treatment or control arm
- The primary analysis is an inequality comparison of the treatment and control arms
- The standard deviation for both arms is 0.22
- A difference ≥ 0.1 is considered clinically significant (i.e., minimal desired detectable difference)
- The difference between the arms is expected to be 0
- Statistical testing will use a two-sided 5% significance level with at least 80% power

At least 154 subjects (77 per treatment arm) are required to analyze the primary effectiveness endpoint with statistical power. To account for up to 20% attrition and other factors, up to 190 subjects (95 per treatment arm) are required to ensure adequate power is maintained for the primary effectiveness endpoint.

7 Analysis of Secondary Endpoints

The secondary endpoints are evaluated at the week 12 follow-up visit and compare the treatment and control arms. Analysis of the secondary endpoints evaluates the following:

- 1. Change in average daily oxygen usage from baseline
- 2. Change in Quality of Life from baseline
 - a. St. George's Respiratory Questionnaire
 - b. Hospital Anxiety and Depression Scale
- 3. Change in Six Minute Walk Test (6MWT) distance from baseline
- 4. Frequency of COPD exacerbation
- 5. COPD or other respiratory condition-related inpatient hospitalization ≥ 24 hours
- 6. Change in average number of steps taken/day (non-hospital days) from baseline
- 7. Mortality due to COPD or other respiratory condition (primary cause of death)
- 8. All-cause mortality

For secondary endpoints 1 and 6, the baseline and week 12 follow-up visit values are the average value during the first and twelfth weeks of the study, respectively. For accuracy, only wake- and wear-filtered ActiGraph data will be used in the analysis.

The assessments used in secondary endpoints 2 and 3 are performed at both the baseline and week 12 follow-up visits.

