The purpose of this Statistical Analysis Plan (SAP) is to summarize the statistical methodologies being used to determine the required sample size for and to analyze all endpoints associated with the use of portable oxygen concentrators (POC) combined with standard of care (SOC) long-term oxygen therapy (LTOT) (treatment) versus SOC alone (control) for 12 weeks among subjects prescribed long term oxygen therapy for diagnosed COPD.

2 Early Study Closure

Due to the outbreak of 2019 Novel Coronavirus (COVID-19) in the United States in March 2020, in particular because of the inherent health risks in this for COPD patients on LTOT and the likely negative impact to their Physical Activity Levels (PAL) (i.e., the patient population and primary endpoint for this study, respectively), the decision was made to prematurely terminate the study effective April 30, 2020. At the time of study closure, 109 of the planned 190 subjects (57%) had been enrolled, of which only 3 were still actively participating in the study.

The following impacts of the COVID-19 outbreak from March 2020 through the final study site closure will be summarized in the final report, where applicable:

- A listing of all subjects impacted by COVID-19-related study disruption, including how they were impacted, along with any related analyses and/or discussions as appropriate
- Analyses and corresponding discussions that address the impacts of the implemented contingency measures (e.g., trial participant discontinuation from investigational product and/or study, alternative procedures used to collect critical safety and/or efficacy data) on the safety and efficacy results for the study
- A summary of the reasons for failing to collect any efficacy endpoints, including identifying specific limitation imposed by COVID-19 leading to the inability to perform the protocol-specified assessment

3 Study Design

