3.1 Study Design/Overview

This is a post-approval, randomized, unblinded, multicenter, parallel group study with 12 weeks of followup. The study will be performed at up to twenty (20) centers in the United States. Up to 190 subjects (95 per treatment arm) will be enrolled in the study.

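### The SAP, written after the trial closed at 109 of 190 patients, still states only the 154-patient, 80% power basis and plans no confidence interval for the primary PAL difference

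*SAP*

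**What the plan says.** SAP 6.2 (Sample Size) assumes an SD of 0.22 in each arm. It states that a difference of at least 0.1 "is considered clinically significant (i.e., minimal desired detectable difference") and adds "The difference between the arms is expected to be 0". It continues "Statistical testing will use a two-sided 5% significance level with at least 80% power", then "At least 154 subjects (77 per treatment arm) are required to analyze the primary effectiveness endpoint with statistical power", and finally "up to 190 subjects (95 per treatment arm) are required to ensure adequate power is maintained for the primary effectiveness endpoint". SAP 3.1 repeats the target: "Up to 190 subjects (95 per treatment arm) will be enrolled in the study".

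SAP 2 (Early Study Closure) records termination effective 30 April 2020: "At the time of study closure, 109 of the planned 190 subjects (57%) had been enrolled". It lists what the final report will add because of COVID-19: a listing of affected subjects, the effect of contingency measures, and "A summary of the reasons for failing to collect any efficacy endpoints". Power and precision are not on the list. SAP 12 shows one version, 1.0, dated 18 August 2020.

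SAP 6 restricts the primary analysis to subjects with PAL at both baseline and week 12. SAP 11.6 plans count, mean, SD, median and range for continuous variables, with a t-test or a Wilcoxon rank-sum test. The SAP contains no confidence interval. Protocol 14.3 mentions 95% intervals only as an option for variables that exist in one arm, plus an exact upper bound for adverse events.

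**The concern.** The SAP was first issued when final enrolment was known, so its sample-size section could have described the trial that was run. It describes only the trial that was planned. The 109 enrolled are already 45 short of the 154 analysable patients (154 − 109 = 45), before any loss to missing PAL values.

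This affects how the result can be read. The plan expects a difference of 0, treats 0.1 as the difference that matters, and SAP 6.1 calls the null hypothesis equality. A non-significant test is therefore the outcome the plan itself anticipates. A p-value above 0.05 cannot separate two situations: the data rule out a difference of 0.1, or there were too few patients to tell. Only an interval for the difference does that, and none is planned. A reader who takes the 80% figure at face value would also give a null result more weight than 109 patients can support.

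**Working it through.** **Inputs.** Difference 0.1, SD 0.22 per arm, two-sided 5%, 80% power and 20% attrition (SAP 6.2); 1:1 allocation (SAP 3.3.4); 109 enrolled (SAP 2). The documents give neither the split of the 109 by arm nor the number with both PAL values. I assume near-equal arms and a loss of 0% to 20%. That gives 109 (55/54) as the ceiling and 109 × 0.8 = 87 (44/43) at the SAP's attrition.

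**Formulas.**
- Standard error: SE = 0.22 × √(1/n₁ + 1/n₂).
- Power: two-sample t-test, noncentral t with n₁ + n₂ − 2 degrees of freedom and noncentrality 0.1/SE.
- Expected half-width of the 95% interval: t(0.975) × SE.
- Detectable difference: the value at which power is 80%.

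**Reproducing the plan.** At 77/77, SE = 0.0355, noncentrality = 2.82 and power = 80.03%. At 76/76, power is 79.50%. The stated 77 per arm is correct.

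**At the reduced size.**

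| | 154 (77/77) | 109 (55/54) | 87 (44/43) |
|---|---|---|---|
| SE | 0.0355 | 0.0421 | 0.0472 |
| Noncentrality | 2.82 | 2.37 | 2.12 |
| Power for 0.1 | 80.0% | 65.2% | 55.4% |
| Chance of missing a true 0.1 | 20% | 35% | 45% |
| Detectable difference, 80% power | 0.100 | 0.119 | 0.134 |
| Expected 95% CI half-width | 0.070 | 0.084 | 0.094 |

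**If the true difference is 0** (400,000 simulated trials per size, normal data, SD 0.22):

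| | 154 | 109 | 87 |
|---|---|---|---|
| CI lies wholly below 0.1 | 80% | 65% | 55% |
| CI contains both 0 and 0.1 | 17% | 32% | 42% |
| CI contains 0.1, among non-significant results | 18% | 34% | 44% |

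**Sensitivity.**
- Uneven arms: 60/49 gives 64.8% and 48/39 gives 55.0%, so the split hardly matters.
- SD 0.20: 73.5% at 109 and 63.5% at 87. SD 0.25: 54.4% and 45.4%.
- SD needed to restore 80% power: about 0.185 at 109 and 0.165 at 87.
- An assumed 30% loss (38/38), which is not a SAP input: 49.8%.
- Wilcoxon test instead of the t-test, normal data (20,000 simulated trials per size): about 63% at 109 and 53% at 87. At a true difference of 0.1 the two tests fall on opposite sides of 5% in about 7% of trials at either size.

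**The case against.** The strongest reply is that nothing here is miscalculated. SAP 2 discloses the closure, SAP 6.2 introduces its assumptions in the past tense, and both SAP 3.1 and 6.2 speak of up to 190, so the text can be read as history. Enrolment had ended, so restating power changes no analysis, and precision will come from the observed data. Protocol 14.1 counts the study a success once mean PAL change has been assessed in both arms, so declared success does not depend on power. The expected difference of 0 also sits awkwardly with Protocol 1, which hypothesises that a POC may make patients more active. No section says that non-significance will be reported as equality. The documents do not justify the SD of 0.22, and at an assumed SD of 0.40 power at 109 would be only 25%. Finally, if count, mean and SD are tabulated by arm, a reader can work out the t-based interval.

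Much of this stands. The planning arithmetic is sound, and any restated figure is conditional on SD 0.22. But enrolment is disclosed while its consequence for the primary test is not, and neither 6.2 nor 3.1 is marked as superseded. A success rule that asks only for PAL change to be assessed makes estimation more important, not less. An interval the reader has to derive is not a pre-specified reading against 0.1, and one matched to the Wilcoxon option cannot be derived from the planned summaries at all.

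**Conclusion.** The concern holds. At its own planning inputs, the trial as run cannot deliver the power the SAP states: 65% at most, and 55% at the SAP's attrition. The detectable difference rises from 0.100 to between 0.119 and 0.134. If there is truly no difference, a third or more of non-significant results would leave 0.1 open, about twice the share at the planned size. No interval is planned that would show the reader which case applies.

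These figures rest on SD 0.22, near-equal arms and a loss of 0% to 20%. The SD matters most, but it would have to be about 0.185 or lower to bring power back to 80% even with no loss. This is a planning basis left without an update, plus a reporting gap, not an error in the original calculation. It should be corrected, and the missing interval is the more important half.

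**What to change.** 1. In SAP 3.1 and 6.2, label the 190-patient, 80% power text as the original plan and add:

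> Enrolment stopped at 109 (Section 2). At the planning inputs (difference 0.1, SD 0.22, two-sided 5% t-test, near-equal arms), power is 65% if all 109 have both PAL values and 55% at 20% attrition (87). The difference detectable at 80% power is 0.119 to 0.134, and the expected 95% CI half-width is 0.084 to 0.094.

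These figures should use the planning SD and difference. Power computed from the observed effect would add nothing to the p-value.

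2. In SAP 6 or 11.6, add:

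> The number analysed is given by arm. The POC-minus-control difference in mean PAL change is reported on the PAL scale with a two-sided 95% CI from the t-test, read against 0 and 0.1. If the Wilcoxon test supplies the p-value, the Hodges-Lehmann shift with its 95% CI is also given. A non-significant test is not taken as equality.

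The cost is wording plus one interval, or two if the Wilcoxon test is used, from data already collected. No patients are added and the primary test is unchanged. The stated power becomes less favourable, and if two intervals are reported and differ, the report must explain why.

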7.1 Hypotheses

7.1.1 Continuous Secondary Endpoints

The null hypothesis for secondary endpoints 1-6 is that there is no difference in the endpoint means for the treatment and control arms (indicating equality). Rejection of the null hypothesis indicates the observed data supports the alternative hypothesis that a difference in the endpoint means exits between the treatment and control arms (indicating inequality). The hypotheses associated with these secondary endpoints are:

H₀:
$$\mu_t - \mu_c = 0$$

H₁: $\mu_t - \mu_c \neq 0$

where μ_t and μ_c are the endpoint means for the treatment and control arms, respectively.

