14.3 Analysis of Secondary and Exploratory Endpoints

The full list of all secondary and exploratory endpoints can be found in Section 5.3. The mean changes from baseline in continuous secondary and other endpoints will be compared between treatment groups via independent samples t-tests, or a non-parametric equivalent as appropriate. General Linear Modeling will be used to assess the impact of potentially influential covariates.

For comparisons of categorical variables, a chi-square test (if appropriate) or Fisher's exact test will be used. Standard logistic regression will also be fit to these endpoints to include center effects and relevant covariates.

For certain variables associated with only one treatment arm, such as POC usage, summaries and estimation, including 95% confidence intervals, may be provided, with no formal hypothesis test performed.

The frequencies of each individual type of adverse event will be summarized along with a 95% exact binomial upper confidence bound. Adverse events, including UADEs, will also be summarized based upon seriousness, severity and relation to the procedure and the device. Individual adverse events will be listed for both groups, including time to event and resolution.

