7.1.2 Categorical Secondary Endpoints

The null hypothesis for secondary endpoints 7 and 8 is that there is no difference in the endpoint proportions for the treatment and control arms (indicating equality). Rejection of the null hypothesis indicates the observed data supports the alternative hypothesis that a difference in the endpoint proportions exits between the treatment and control arms (indicating inequality). The hypotheses associated with these secondary endpoints are:

$$H_0$$
: $p_t - p_c = 0$
 H_1 : $p_t - p_c \neq 0$

where p_t and p_c are the endpoint proportions for the treatment and control arms, respectively.

8 Analysis of Exploratory Endpoints

The exploratory endpoints are evaluated at the week 12 follow-up visit and compare the treatment and control arms. Analysis of the exploratory endpoints evaluates the following:

- 1. Time from enrollment to hospitalization for a COPD or other respiratory condition-related inpatient hospitalization ≥ 24 hours
- 2. Number of days in hospital for COPD or other respiratory condition-related inpatient hospitalization ≥ 24 hours
- 3. All-cause unplanned hospitalizations
- 4. Change in average daily activity duration and intensity
- 5. Change in average energy expenditure/day

Exploratory endpoint 1 will be analyzed with a Cox proportional hazard model, using time to hospitalization as the response and treatment arm, center, age, and baseline 6MWT as predictors. The model will be summarized with regression coefficient estimates and standard deviations.

For exploratory endpoint 4, the baseline and week 12 follow-up visit values are the average value during the first and twelfth weeks of the study, respectively. For accuracy, only wake- and wear-filtered ActiGraph data will be used in the analysis. Exploratory endpoint 4 will be summarized in the following ways:

- Change in average duration per day at each intensity from baseline to the week 12 follow-up visit
- Average duration per day at each intensity over 12 weeks
- Change in percentage of time spent engaging in Sedentary to Very Low Physical Activity (SVLPA) from baseline to the week 12 follow-up visit

 Proportion of subjects engaging in Moderate to Vigorous Physical Activity (MVPA) at the week 12 follow-up visit who did not at baseline

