11.1 Analysis Sets

11.1.1 Intention-to-Treat

The intention-to-treat analysis set (ITT) consists of randomized subjects who begin long-term oxygen therapy, with or without a POC, receive an ActiGraph device, and have at least baseline ActiGraph data. The ITT analysis set will be used as the primary analysis set in analyzing all endpoints.

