11.6 Data Summaries

Unless otherwise stated, data will be summarized as followed:

- Continuous variables will be summarized with the count, mean, standard deviation, median, and range. Hypothesis testing will use the t-test (or Wilcoxon rank-sum test).
- Categorical variables will be summarized with counts and percentages. Hypothesis testing will
 use the chi-squared test (or Fisher exact test).
- Level of significance (α) for statistical testing will be 0.05 and two-sided.

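### SAP 7.1.1 compares exacerbation frequency and respiratory hospitalisation as raw means with no term for follow-up time, so dropout that differs by arm can bias either comparison in either direction

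*SAP*

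**What the plan says.** SAP 7 lists endpoint 4 as "Frequency of COPD exacerbation" and endpoint 5 as "COPD or other respiratory condition-related inpatient hospitalization ≥ 24 hours". It gives no unit or denominator for either, and does not say whether endpoint 5 is a count or yes/no.

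SAP 7.1.1, on continuous endpoints, covers both: "The null hypothesis for secondary endpoints 1-6 is that there is no difference in the endpoint means for the treatment and control arms". SAP 7.1.2 keeps proportions for the two mortality endpoints: "The null hypothesis for secondary endpoints 7 and 8 is that there is no difference in the endpoint proportions". SAP 11.6 assigns continuous variables to a t-test or Wilcoxon rank-sum test at two-sided 0.05.

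On the analysis set, SAP 11.1.1 says: "The ITT analysis set will be used as the primary analysis set in analyzing all endpoints". Membership needs randomisation, the start of oxygen therapy, an ActiGraph device and baseline ActiGraph data. It does not need follow-up to week 12. The restriction to patients with both baseline and week 12 values (SAP 6) is stated for the primary endpoint only.

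Protocol 14.3 sends categorical variables to chi-square or Fisher tests and adds: "Standard logistic regression will also be fit to these endpoints to include center effects and relevant covariates". That has no follow-up-time term either. Protocol 14.4 promises a missing-data sensitivity analysis for every endpoint; SAP 11.5 provides one for the primary endpoint only.

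**The concern.** Endpoint 4 is an event count, and endpoint 5 is a count or an indicator. Both accumulate with time observed. Under the stated tests, a patient who leaves event-free at week 3 contributes the same zero as one followed event-free for 12 weeks. The Wilcoxon option does not help: it also ignores follow-up time, and with events this infrequent most values tie at zero.

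Equal dropout cancels out of the ratio of means. Unequal dropout does not. The trial is unblinded and only one arm receives a POC, so differential dropout is plausible. More loss in the POC arm would exaggerate a benefit; more loss in the control arm would hide one. Both endpoints are formally tested at 0.05, and only 109 of 190 planned patients were enrolled, so there is little power to spare.

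**Working it through.** **The plan's own figure.** The documents give no event rate, power or sample size for endpoints 4 and 5. The only sample-size figure, 77 per arm for PAL, reproduces: 2 × (1.96 + 0.8416)² × 0.22² / 0.1² = 75.98, so 76 by the normal formula and 77 with the t correction. It says nothing about event endpoints.

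**Inputs from the documents.** Follow-up of 12 weeks; 1:1 allocation; up to 20% attrition overall, not split by arm (SAP 6.2); 109 enrolled (SAP 2).

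**Assumptions.** 55 per arm; dropout of 10% in one arm and 30% in the other, which averages the planned 20%; the event rates and dispersion stated below.

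**Bias with equal true rates.** Let d be the proportion dropping out.
- Dropout times uniform over 12 weeks: mean share of follow-up observed = 1 − d/2. For 10% this is 0.95; for 30%, 0.85. Ratio of mean counts: 0.85/0.95 = 0.895 or 0.95/0.85 = 1.118, a shift of 10-12%.
- All dropout in the first 6 weeks: leavers are observed for a quarter of follow-up on average, so the share is 1 − 0.75d. For 10% this is 0.925; for 30%, 0.775. Ratio: 0.838 or 1.194, a shift of 16-19%.
- A milder split, 15% versus 25%, uniform: 0.875/0.925 = 0.946 or 0.925/0.875 = 1.057, a shift of 5-6%.

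**Type I error and power.** Simulation of gamma-Poisson counts, 20,000 trials per row, 55 per arm, control rate 0.5 events per 12 weeks, dispersion 1, uniform dropout times. The t-test on raw counts is set against events per person-time with a robust variance. Power is for a true rate ratio of 0.5.

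| Dropout POC / control | Type I, t-test | Type I, rate | Apparent ratio | Power, t-test | Power, rate |
|---|---|---|---|---|---|
| 20% / 20% | 4.8% | 5.7% | 0.50 | 39% | 43% |
| 10% / 30% | 6.2% | 6.1% | 0.56 | 29% | 43% |
| 30% / 10% | 6.0% | 5.7% | 0.45 | 51% | 42% |

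With all dropout in the first 6 weeks, t-test type I error for the unequal splits is just under 8%. The rate estimate stays at 0.50 throughout.

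The power gap in the second row is 14 points. About 3 to 4 of these are present with equal dropout and come from the choice of test (the rate test's size is also slightly above 5%). The other 10 or so come from unequal follow-up.

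**Wider range.** With dispersion 0.5, 54 versus 55 patients and rates of 0.25-1.0 events per 12 weeks, t-test type I error for a 10/30 split in either direction is 5.5-7.3% (uniform) and 6.5-10.8% (early). It reaches 17.5% only with a 5/35 split, early dropout and the highest rate. At 0.1 events per 12 weeks it stays at 5.0-6.7%, and the person-time test is then conservative, at about 2%.

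**The case against.** **Unequal dropout is not shown.** This stands. The documents report no dropout by arm. The 20% allowance was made for the PAL sample size, and a patient without usable week 12 ActiGraph data may still have full event follow-up. Protocol 13.2.1 seeks adverse events at every encounter and by medical-record review, and Protocol 12.2 asks for an in-person final visit at withdrawal. Only 3 of the 109 enrolled were still active at closure, so early termination cut off little follow-up. A 10/30 split may overstate the imbalance in time at risk.

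**The Cox model already uses follow-up time.** Partly right. SAP 8 plans one for time to respiratory hospitalisation. It is exploratory, covers the first event only and leaves exacerbations untouched.

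**Frequency could mean a rate, or the analysis could be of completers.** Neither is stated. SAP 7 says "The secondary endpoints are evaluated at the week 12 follow-up visit and compare the treatment and control arms", but it does not limit the analysis to patients who reach that visit. If it did, unequal dropout would act through selection instead of exposure.

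**Two stronger readings do not hold.** A reader might infer that the plan is likely to yield a false positive on these endpoints. At the enrolled size a 10% shift is small against sampling error, and type I error moves little unless dropout is both early and very unequal. A reader might also infer that the SAP flatly contradicts the protocol on endpoint 5. Protocol 14.3 speaks of categorical variables without naming endpoint 5, so there is a conflict only if that endpoint is yes/no, and the documents do not say.

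**Conclusion.** The gap is real: two event endpoints are tested as raw means, in a set that keeps early leavers, with no person-time term. If dropout differs by arm, this can produce or hide a difference; the documents do not show that it did. For an assumed 10% versus 30% split, the ratio of mean counts is off by 10-12% (16-19% if dropout is early). Type I error is about 6-8% in the main scenario. Power is about 29% instead of 43% when the control arm loses more; in the reverse case the t-test appears more powerful (51% versus 42%) only because it overstates the effect. Equal dropout removes the bias. These sizes rest on assumed rates, dispersion and dropout.

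These are secondary endpoints with no stated power target, so the change is advisable but does not bear on the primary result.

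**What to change.** 1. In SAP 7.1.1, replace endpoints 1-6 by endpoints 1-3 and 6.
2. Endpoint 4: state what counts as one exacerbation and when time at risk ends (week 12 visit, withdrawal or death). Analyse the count with a negative binomial model, or Poisson with robust standard errors, with log follow-up time as offset. Report the rate ratio and 95% CI.
3. Endpoint 5: state whether it is a count or a first event, and test it with a method that uses time at risk: the same rate model for counts, or the Cox model already specified in SAP 8 for time to first event. Give the proportion hospitalised, with Fisher or chi-square, as a supporting summary only. As the main test it would ignore follow-up time just as the t-test does.
4. Report follow-up time and dropout by arm, and add the sensitivity analysis for these endpoints that Protocol 14.4 promises. An offset corrects for unequal exposure but not for dropout related to the patient's own risk.

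The cost is SAP wording and a few lines of code. The planned Cox analysis already needs hospitalisation and censoring dates, and Protocol 14.3 already calls for time to event in the adverse event listings. SAP version 1.0 is dated after study closure, so the amendment should record its date and whether comparisons by arm had been seen.
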